### 4.0 Study Endpoints

- 4.1 The primary study endpoint is COVID vaccine uptake and series completion. The secondary study endpoint is change in vaccine hesitancy, vaccine confidence, and change in knowledge, attitudes, and beliefs.
- 4.2 N/A

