### 6.0 **Procedures Involved**

6.1 This study will consist of three distinct aims to develop and test the TT-C intervention for COVID vaccine hesitant AA-YA. Aims 2 and 3 procedures are premised on the formative data collected in Aim 1.

Aim 3: Conduct a hybrid type 1 effectiveness implementation 2-arm randomized controlled trial with 360 AA-YA from AL, NC, and GA.

6.2 Enrollment: After screening eligible and agreeing to be contacted, eligible responses will be reviewed individually by study staff to determine authenticity and legitimacy. In addition to eligibility criteria, staff will review bot detection values as well as location based on IP address & latitude/longitude. If determined eligible, staff complete the Verification CRF and REDCap will email the individual with a unique consent form link to complete. Once completed, REDCap will send the baseline survey linked to their unique ID in REDCap.

After the baseline survey is complete, study staff will randomize the participant with the Randomization CRF to either the intervention or control group. Based on the study arm, study staff will either email the participant with the developed SOC materials or email the participant with a unique link to create their account for the TT-C app. If SOC, the participant will be compensated at this time.

If participant is randomized to intervention arm, they will be prompted to create their account with the provided link, then will be

> directed to download and login to the TT-C app. Once account creation is confirmed in the administrator portal, study staff will compensate the participant for enrolling.

Randomization: RCT participants will be randomized via block randomization into the control condition and TT-C (remote), each with a balanced 180 participants. Assignment will be stratified by state to achieve balance between intervention and control participants within a given study state.

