Locator/Contact Information Collection: Once consented and enrolled, designated site study staff will collect contact information from the participant. Participants will be asked to provide contact information through which they can be reached. Participants will also be asked to provide valid contact information for two family members and/or friends who can be called in the event the participant cannot be reached by phone or email. Participants will be asked if messages can be left at the numbers provided. Study staff will not leave messages unless expressly permitted to do so by the participant which also will be documented. If permission is given to leave messages, site staff will assure participants that messages left with a family member or friend will only ask the participant to contact study staff and will not include any protected health information or information related to study participation.

The Contact Information Worksheet will not contain any study data and will be maintained under double locks at the study site, separate from all study records, with access limited to designated site research personnel.

Optional Monkeypox Module: Participants will also be given the opportunity to complete an optional set of questions about Monkeypox immediately following the baseline survey.

TT-C arm: Once enrolled, participants will be emailed a unique link to create their TT-C account and instructions on how to download the TT-C (remote) app from the iOS or Google Play store. They will be asked to complete the intervention within one month. Participants will be compensated for completing the baseline survey and reminded that they will be asked to return (virtually) in 1 and 3 months for follow-up.

Standard of Care arm: Research staff will provide COVID vaccine materials from the CDC to those participants in the SOC arm. Participants will be compensated for completing the baseline survey and reminded that they will be asked to complete 1 and 3-month follow-up surveys. To provide the maximum benefit through this trial, after the completion of the data collection associated with the

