> primary RCT, those randomized to the control arm who still report VH will be offered the opportunity to accept the TT-C intervention delivered remotely. These participants will be asked to use the app for one month and complete follow-up surveys at their 4- and 6month time points (same surveys used for 1 and 3M). These participants will be compensated for survey completion.

Participants will also be asked to complete exit interviews to discuss their experience with the intervention and/or their knowledge, attitudes, and perceptions of COVID-19 vaccination.

6.3 Research Staff Training: All proposed study staff have participated in the required trainings in participation and conduct of studies that involve human subjects, and any future study staff will do so upon hiring. Training for all research staff includes (but is not limited to): an overview of the study; study procedures and human subjects issues (informed consent process, confidentiality); a demonstration of all technology components; methods for establishing comfort with the sensitive issues that may arise in the course of the focus groups or assessments; Human Subjects Protection; Good Clinical Practice; informed consent; quality management; confidentiality; and reporting of adverse events.

Intervention Monitoring/Quality Control: Because the TT-C intervention is an app, intervention fidelity is assured for all activities except for the reflection activities and facilitation of vaccination appointments.

Data Platform Security: We use SSL encryption for transfers of information online and data will be stored in the secure, HIPAA-compliant servers of the Florida State University. The CASI data will be stored in a secure database at Qualtrics and REDCap.

Qualtrics and REDCap use Transport Layer Security (TLS) encryption (also known as Hypertext Transfer Protocol Secure (HTTPS)) for all transmitted data. Survey data are protected with passwords and HTTPS referrer checking. The data is hosted by third party data centers that are Statement on Standards for Attestation Engagements (SSAE)-16 Service Organization Control (SOC) II certified. All data at rest are encrypted, and data on deprecated hard drives are destroyed by U.S. Department of Defense methods and delivered to a third-party data destruction service.

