Effectiveness Outcomes: Primary effectiveness outcomes are COVID vaccine uptake and completion of series; secondary effectiveness outcomes are VH, confidence, and knowledge, attitudes, and beliefs. We will also collect implementation outcomes, SCT constructs targeted by TT-C, COVID-specific risks and behaviors and pertinent constructs that have been validated in the extant literature on AA-YA (Table 5).

Analyses of Effectiveness Data: We will use logistic regression to determine the effect of treatment arm on the probability of vaccination uptake (yes/no) and COVID vaccine series completion (yes/no) at month three. We will determine whether the overall 2degree-of-freedom test for differences among treatments is statistically significant. If so, we will examine the parameter estimates and standard errors to determine where difference lie between the three arms. We will focus on the odds ratios for comparing the probability of infection in each of the two treatment groups with the probability in the controls. The secondary outcomes of VH, vaccine confidence and vaccine knowledge, attitudes and beliefs will all be assessed using previously validated scale scores, each of which will consist of the continuous sum of responses to a series of questions with Likert scale responses. We will use linear regression models with treatment group as the exposure to determine whether secondary outcomes vary among treatment groups. Lastly, we use the causal mediation framework proposed by Valeri and Vanderweele to understand mechanisms for any intervention effects through each of our hypothesized mediators. We will use the gformula command in Stata which uses the mediational g-formula to estimate the controlled direct, natural direct, and natural mediated (indirect) effects.59

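### The secondary scale models in 17.1 name treatment arm alone and no visit; fixing month 3 and adding baseline score and state would settle the estimand and gain precision

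*Combined protocol and SAP*

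**What the plan says.** **Model.** Section 17.1 (Analyses of Effectiveness Data) gives the secondary analysis in one sentence: "We will use linear regression models with treatment group as the exposure to determine whether secondary outcomes vary among treatment groups". No other term is named.

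**Visit.** In the same paragraph a time point is attached to the two logistic outcomes only: "vaccination uptake (yes/no) and COVID vaccine series completion (yes/no) at month three". None is given for the scales. Section 6.2 schedules two follow-ups; control participants are "reminded that they will be asked to complete 1 and 3-month follow-up surveys", and the intervention arm has the same two. When 6.2 describes the later surveys for control participants who take up the app, it adds "same surveys used for 1 and 3M". The scales are therefore presumably available at both visits.

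**Form of the outcome.** Section 4.1: "The secondary study endpoint is change in vaccine hesitancy, vaccine confidence, and change in knowledge, attitudes, and beliefs". Section 17.1 describes scale scores, "each of which will consist of the continuous sum of responses to a series of questions with Likert scale responses", and does not mention change.

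**Baseline and state.** Section 6.2 (Enrollment): "After the baseline survey is complete, study staff will randomize the participant with the Randomization CRF". Section 6.2 (Randomization): "Assignment will be stratified by state to achieve balance between intervention and control participants within a given study state". Neither the baseline score nor state is named as a term in any outcome model. Section 17.2 says that comparability between states will be examined, with separate analyses if they differ. The Missing Data text in 17.1 refers to covariates without naming any.

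**The concern.** Two analysts following 17.1 could fit different models to the same scale: month 1 or month 3, follow-up score or change. These are different estimands and their estimates can diverge, because a chance baseline difference between arms pushes the score and change analyses in opposite directions.

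The plan also leaves free precision unused. A change endpoint implies that baseline scores are collected, and the baseline survey comes before randomization, so the score is a legitimate covariate. State is recorded for every participant because assignment is stratified on it. At stake are the width of the intervals and the clarity of the only named secondary effectiveness outcomes. The validity of the randomized comparison is not in question.

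**Working it through.** **Plan's own figures (17.1, sample size).** With 360 randomized and 15% lost, 360 × 0.85 = 306, or 153 per arm. At 153 per arm, two-sided 0.05, a 30% control rate and a 15.5-point difference, power is 80.2%, so the stated 80% reproduces. That calculation is for vaccine uptake. The documents give no SD, effect size, correlation or power for the scales, so what follows is an illustration.

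**Inputs.** n = 153 per arm (primary-endpoint completers; scale completers are not stated). Correlation r between baseline and follow-up is assumed at 0.3 to 0.8. Baseline and follow-up variances are assumed equal.

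**Formulas.** Variance of the arm difference relative to the unadjusted score:
- follow-up score: 1
- change: 2(1 − r)
- baseline-adjusted: 1 − r²

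Let m be the smaller of 1 and 2(1 − r). Interval narrowing = 1 − √[(1 − r²)/m]. Equivalent sample size = 306 × m/(1 − r²). Detectable difference at 80% power, in SD units = 2.80 × √(2/153 × relative variance).

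| r | Score | Change | Adjusted | Narrowing | Equivalent N | Detectable: better unadjusted v adjusted |
|---|---|---|---|---|---|---|
| 0.3 | 1 | 1.40 | 0.91 | 4.6% | 336 | 0.320 v 0.306 |
| 0.5 | 1 | 1.00 | 0.75 | 13.4% | 408 | 0.320 v 0.277 |
| 0.7 | 1 | 0.60 | 0.51 | 7.8% | 360 | 0.248 v 0.229 |
| 0.8 | 1 | 0.40 | 0.36 | 5.1% | 340 | 0.203 v 0.192 |

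The narrowing does not depend on n. It peaks at r = 0.5 and is about 5% at both ends of the range.

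**Unequal variances.** If the baseline SD is k times the follow-up SD, the relative variance of change is 1 + k² − 2rk. This exceeds the adjusted value by (k − r)², which is never negative. In large samples the adjusted form therefore never does worse, though the size of its gain over change depends on k.

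**Chance baseline imbalance.** The 95% range is ±1.96 × √(2/153) = ±0.224 SD. A difference d moves the score estimate by r × d and the change estimate by −(1 − r) × d. At r = 0.5 and d = 0.22 that is +0.11 and −0.11 SD. Baseline adjustment removes both shifts.

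**Score or change, once baseline is in the model.** Subtracting baseline from the outcome lowers the baseline coefficient by exactly 1 and leaves the arm coefficient unchanged. The choice between score and change then no longer affects the arm estimate.

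**State in the linear models.** If state explains 1, 5 or 10% of outcome variance (assumed), leaving it out gives an actual two-sided error rate of about 0.049, 0.044 or 0.039, which is conservative.

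**State in the primary logistic models.** The simulation assumed 51 participants per arm in each of three states, a common odds ratio of 2.13, Wald tests and 20,000 replicates. State control rates are assumed.

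| Control rates by state | Power without v with state | Type I error without v with state | Mean SE of log odds ratio without v with state |
|---|---|---|---|
| 15/20/25% | 82.1 v 82.5% | 4.4 v 4.6% | 0.266 v 0.269 |
| 10/20/35% | 79.7 v 81.8% | 4.1 v 4.9% | 0.260 v 0.273 |
| 5/20/40% | 72.8 v 77.8% | 3.3 v 4.6% | 0.261 v 0.286 |

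Omitting state is valid and slightly conservative. Including it does not narrow the log odds ratio interval, and the power gain is small unless state rates differ widely.

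**The case against.** Several points on the other side stand.

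- **Covariates are not excluded.** Calling treatment group the exposure names the variable of interest and does not make it the sole predictor. The Missing Data text in 17.1 contemplates covariates. What is supported is that none is named for these models.
- **4.1 and 17.1 need not conflict.** The sum-score clause can be taken as saying how each scale is built, and 4.1 as saying that its change is the endpoint. A reader might infer a contradiction; the text does not compel one. It does not state the combined reading either.
- **Month 3 is the natural default.** It is the time point of the primary outcomes and the end of RCT follow-up. It is still not stated for the scales.
- **State is not ignored.** Section 17.2 looks at comparability between states. That leads to conditional separate analyses, which is different from a model term.
- **The gain rests on assumptions.** Section 1.0 lists expressed hesitancy among the RCT criteria, which may restrict baseline spread on the hesitancy scale and lower r.
- **Some material is not in the supplied text.** Section 17.1 points to a Table 5 and to a separate Statistical Analysis Plan. The finding applies to the wording available.

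A stronger inference is tempting: that the open wording inflates false positives. If someone tried score and change at both months and kept the best, simulation under the null with equal correlations gives 15 to 16% per scale instead of 5%. That is a worst case. It falls to about 14% if the two follow-ups correlate more strongly with each other than with baseline (0.6, 0.5 and 0.8 assumed). If only the form is chosen at month 3 it is about 9%, and if only the month is chosen, using scores, about 8 to 9%. Nothing in the documents suggests that such a choice is planned.

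**Conclusion.** The point holds as a gap in specification with a modest precision cost. The visit, the form of the outcome and the covariates are not stated for the secondary scales, and two variables that would help, baseline score and state, are not named as terms.

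The size is an interval about 5 to 13% wider than necessary, for r between 0.3 and 0.8 with equal variances. It is 13% only near r = 0.5. Both inputs are assumptions.

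A reader might go further and call the unadjusted secondary comparison biased, or the primary analysis wrong for omitting state. The documents support neither: comparing randomized arms without adjustment is valid, and leaving out the stratification factor errs slightly on the conservative side. The change should be made for the secondary models. For the primary models it is a minor improvement.

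**What to change.** In 17.1, state that each secondary scale score at month 3 is analysed by linear regression on treatment arm, that scale's own baseline score and state, and that the month-1 analysis is supportive. Name the same model in 4.1. The arm estimate is then the same whether the outcome is called score or change, so the two sections agree.

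Optionally, add state to the two primary logistic models to follow the stratified design, and label the odds ratio as conditional on state. This changes what the primary odds ratio measures, so it is more than an edit of wording and should be decided deliberately.

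**Cost.** No participants, surveys or visits are added. State is already recorded, and the change endpoint implies that baseline scores are collected. A participant with a missing baseline scale score leaves the adjusted model. On the change reading that loss already exists; on the follow-up-score reading it is new. It should be small, because the baseline survey is completed before randomization, so the loss comes mainly from skipped items.

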Missing Data: In sensitivity analyses, we will also use inverse probability of treatment weights (IPTW) to account for missing data and potential differential retention between study arms over the study period. We will weight outcome models using stabilized inverse probability-of-censoring weights that include treatment arm as a predictor to account for differential loss to follow up. Pooled logistic regression models will be used to estimate the numerator and denominator of censoring weights, and weights will be multiplied over time. The denominator will be calculated using a logistic regression model for loss to follow up, including treatment arm. Weights will be stabilized to reduce potential bias from extreme weights. Numerator weights for the stabilized IPTW will be estimated using a logistic regression model for loss to follow up without covariates. Distributions will be examined to ensure weights have a mean of 1; extreme weights that may introduce bias will be trimmed by cutting the top or bottom 1%. Analogous weight will be calculated for missing data, including relevant covariates, and will be multiplied by censoring weights.

Several procedures will be used to conduct data analysis when data for either outcomes or covariates are missing. The first step will be to assess the extent and pattern of missing data. If data are missing for only a few cases, then data analysis will be conducted only on study participants with complete data. However, when such a

> strategy would result in loss of data from a substantial proportion of participants, or if this approach would lead to biased or inaccurate results, then some form of imputation will be performed. The form of imputation used will depend on the nature of the data that are missing. For example, data that are collected repeatedly might be imputed using the "last value carried forward" method; and in some instances, interpolation between neighboring points might also be used.

When the primary endpoint is missing, one data analysis will be conducted using only cases with the endpoint. Subsequent analysis will be done where missing endpoints are imputed. Hot-deck imputation or regression imputation may also be used in this context.

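### Fitted with the one predictor named, the loss-to-follow-up weight cannot change the arm odds ratio, and imputation of missing primary endpoints has no stated variance method

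*Combined protocol and SAP*

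**What the plan says.** All of this is in section 17.1 of the combined protocol and SAP, under Missing Data, unless another section is given.

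- **Status of the weighting.** "In sensitivity analyses, we will also use inverse probability of treatment weights (IPTW) to account for missing data and potential differential retention".
- **Loss-to-follow-up weight.** The outcome models are to be weighted by stabilised censoring "weights that include treatment arm as a predictor to account for differential loss to follow up". The denominator is described thus: "The denominator will be calculated using a logistic regression model for loss to follow up, including treatment arm". For the numerator: "Numerator weights for the stabilized IPTW will be estimated using a logistic regression model for loss to follow up without covariates". Weights are estimated by pooled logistic models and multiplied over time, and "extreme weights that may introduce bias will be trimmed by cutting the top or bottom 1" per cent.
- **Second weight.** "Analogous weight will be calculated for missing data, including relevant covariates, and will be multiplied by censoring weights".
- **Missing primary endpoint.** "When the primary endpoint is missing, one data analysis will be conducted using only cases with the endpoint". Then: "Subsequent analysis will be done where missing endpoints are imputed". Hot-deck and regression imputation are offered as options for this. For repeated data, last value carried forward and interpolation are given as examples. Multiple imputation, Rubin's rules, the bootstrap or any other variance method for imputed data appears nowhere.
- **Outcome model.** Under Analyses of Effectiveness Data, vaccination at month three is analysed by logistic regression on treatment arm. No other covariate is named.

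**The concern.** These analyses exist to show whether the complete-case result survives about 15% loss, which is 54 of 360 participants. A sensitivity analysis can do that only if it is able to give a different answer when loss is selective. A loss weight that depends on arm alone cannot. Its agreement with the complete-case odds ratio would follow from algebra, yet could be reported as robustness.

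The imputed analysis carries a different risk. If imputed values are treated as observed, it can look more precise than the data allow. The plan does not say whether values are imputed once, whether donors come from the same arm, or how the standard error is obtained.

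**Working it through.** **Inputs.** From section 17.1: 15% loss assumed equal across arms, 306 evaluable (153 per arm), two-sided alpha 0.05, 80% power. From section 6.2: 180 randomised per arm, stratified by state.

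**The plan's own figures.** 360 x 0.85 = 306, so 27 are lost per arm. With 153 per arm, the detectable differences at control rates of 10, 20, 30 and 50% come to 11.6, 14.2, 15.5 and 15.8 points. The plan's figures, read from text in which old and new digits run together, are about 12, 14, 15.5 and 16. They reproduce.

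**Step 1: the arm-only weight cancels.** Let every retained participant in an arm have weight w. The weighted proportion is sum(w*y)/sum(w) = w*sum(y)/(w*n) = sum(y)/n, the unweighted proportion. For example, with 20% and 10% loss the weights are 0.85/0.80 = 1.06 and 0.85/0.90 = 0.94. Each multiplies events and non-events in its arm equally, so the odds do not move. In 200 simulated trials with two follow-up intervals, the largest change in the log odds ratio was 1e-14, also with time or arm-by-time in the pooled model. Trimming adds no adjustment when there is one value per arm. In one simulated trial with 77% retained, adding a baseline covariate related to both loss and outcome moved the log odds ratio from 0.529 to 0.623.

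**Step 2: what the inert factor leaves uncorrected.** There is no true effect. Odds ratios (OR) are per SD of baseline hesitancy and are assumptions. Each row is 20,000 trials with a single-interval loss model. Entries are bias in percentage points relative to full data.

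| Assumed scenario | Complete case | Arm only | Arm + hesitancy | With arm-by-hesitancy |
|---|---|---|---|---|
| Both arms, loss 20% v 10%, uptake 20%, OR 2 for loss and 0.5 for uptake | +0.60 | +0.60 | -0.01 | not run |
| Same, OR 3 and 0.35 | +1.18 | +1.18 | +0.01 | not run |
| TT-C arm only, loss 15%, uptake 20%, OR 3 and 0.5 | +1.28 | +1.28 | +1.35 | -0.02 |
| TT-C arm only, loss 15%, uptake 30%, OR 3 and 0.35 | +2.35 | +2.35 | +2.47 | 0.00 |

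Complete-case type I error in the four rows is 4.8, 5.9, 5.6 and 7.3%, and the arm-only weight leaves it there. With equal 15% loss and the same OR of 2 in both arms, the bias is -0.02. Numerical integration over uptake 10-30%, uptake OR 0.35-0.7 and loss OR 1.5-3, with hesitancy driving loss in TT-C only, gives 0.18 to 2.34 points.

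**Step 3: imputation at 15% loss.** With one within-arm hot-deck draw, the variance of an arm proportion is proportional to 1/153 + 27/180^2. The naive analysis uses 1/180. The ratio is 180/153 + 27/180 = 1.33, so the standard error is too small by 1 - 1/sqrt(1.33) = 13%. The nominal 1.96 then acts as 1.96 x 0.868 = 1.70, a two-sided error of about 8.9%. Simulation at uptake 10, 20 and 30% (400,000 replicates) gave 8.5, 8.7 and 8.9%, against 4.5, 4.9 and 5.0% for complete case. A separate coverage check gave 91-92% for a nominal 95% interval.

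Other choices that the plan leaves open:

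- **Hot-deck with donors pooled across arms:** type I error 4.7-5.0%. The difference shrinks by 27/180 = 15%, so 12 points become 10.2, and power falls by about 7 points.
- **Regression imputation entered as fractions:** standard error too small by 1 - sqrt(153/180) = 8%; type I error 6.6-7.1%.
- **Regression imputation rounded to yes/no:** about 4-4.5%, with 1-3 points of power lost.
- **Multiple imputation within arm, Rubin's rules:** 4.4-5.0% without covariates. With hesitancy, state and age, in the four scenarios of step 2, 4.3-4.8% with bias of +0.03 to +0.09.

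**The case against.** The strongest reply is that the plan applies a product of two weights, and the second is to contain relevant covariates. The paragraph's stated aim covers both missing data and retention, so it is natural to read the second weight as reaching participants lost to follow-up. The word used for the denominator is not exhaustive, and trimming extremes makes little sense for weights with one value per arm. This stands. A reader might infer that the whole weighted analysis is inert, and the documents do not support that. In the two scenarios where hesitancy acts in both arms, a second weight that covers lost participants and contains arm and hesitancy brings the bias to 0.0. If it covers only other gaps in the data, the bias stays. The text does not settle which.

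A reader might also infer that the plan commits to single imputation and so inflates type I error. It does not. Its wording is permissive, hot-deck and regression draws can be repeated and combined, and the 8-9% figure needs three choices that the plan never makes: one draw, donors within arm, and a naive standard error. Carrying forward a vaccination already reported at month 1 is also partly covered by the last-value example.

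Finally, the selective-loss biases are small beside detectable differences of 12-16 points, and the largest needs strong assumed associations in one arm only. That is correct and limits the weight of the point. Section 17.1 refers deviations to a Statistical Analysis Plan, but the supplied text has no separate section that names the covariates or the variance method.

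**Conclusion.** The point holds as a limited one about the sensitivity and imputed analyses. Arm is the only predictor named for loss to follow-up. Fitted as named, that factor is exactly inert for the planned logistic model on arm, and this needs no assumption beyond an outcome model without further covariates. Whether the combined weight corrects anything depends on a second weight whose content and coverage are unspecified.

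For imputation, the defect is the missing variance method. At 15% loss, type I error runs from about 4% to about 9% depending on choices left open, and the option that keeps it near 5% by pooling donors dilutes the effect by 15%.

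The complete-case analysis uses neither method and is not affected by this point. Nor do the documents show that its result will be materially biased: the 0 to 2.3 points rest on assumed links between hesitancy, loss and uptake. The matter is worth settling before analysis and is not a threat to the trial's main conclusion.

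**What to change.** **Weights.** Put arm and baseline hesitancy in the loss-to-follow-up denominator with an arm-by-hesitancy term, or fit a parsimonious model by arm. Add state and age if the fit is stable. The interaction matters because main effects alone did not help when hesitancy drove loss in one arm. State that the weights cover participants lost to follow-up, list the covariates of the second weight, and use robust standard errors. Month-1 responses are optional for later loss.

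**Imputation.** For missing primary endpoints, specify multiple imputation within arm with the same variables and Rubin's rules, in place of the hot-deck, regression and last-value options. Keep vaccination already reported at month 1 as known uptake.

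**Cost.** Plan wording and modest programming. Hesitancy change is a secondary endpoint (section 4.1), state is the stratifier (6.2), age is an eligibility item (10.2), and month-1 surveys are planned (6.2), so no new data are needed. In the single-interval simulations, without month-1 terms, weighted standard errors were about 1% wider than complete case. With about 27 losses per arm, the median ratio of largest to mean weight was 1.85-2.80 and its 99th percentile 4.3-9.6, so the model should stay small. Multiple-imputation standard errors about equalled complete-case ones. The cost of adding month-1 terms was not tested.
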